The liver diseases frequently occur in China. For various reasons, the chronic liver diseases are not controlled in time, and then develop gradually into liver fibrosis and cirrhosis. Without effective treatment, the advanced liver cirrhosis seriously influences the quality of life of patients, and places an intolerable burden on family and society. At present, the scholar generally thought that the liver fibrosis at early stage is reversible. Therefore, if the liver fibrosis in patients with chronic liver diseases can be accurately evaluated at early stage and be treated in time, so we can stop the progress of diseases and reduce the occurrence of liver cirrhosis and liver cancer.

For many years, liver biopsy is still as “golden standard” for diagnosis of liver inflammation and fibrosis. However, with its invasiveness, potential risks and some complications, liver biopsy is limited in clinical application due to the poor acceptability and repeatability. In recent years, the liver fibrosis cannot directly and accurately diagnose via the various diagnostic model using serological biomarkers (e.g. FIBROTEST and FIBROSIS PREDICTIVE APRI) and medical imaging technology (e.g. ultrasonic B, CT and MRI).

Transient elastography is a new technology in the field of ultrasonic imaging. Liver stiffness measurement (LSM) is based on the relationship between speed of the spread of acoustic wave and stiffness of tissues. It utilizes specific probes to send out controlled low-frequency shear waves, the waves signals transmit through liver tissues, a high-frequency signals to track the transmitting process of shear wave in the liver and the value of liver stiffness (KPa) is quickly calculated with reference to a built-in liver histological model, which provides a quantitative standard for diagnosis of liver fibrosis of chronic liver disease. The bigger LSM value means the faster transmission of shear wave, and the harder of determined tissue.

At present, FibroScan (France, Echosens) as a transient elastography product, has been widely applied in clinical practice. Many studies both at home and abroad on chronic hepatitis B (CHB) and chronic hepatitis C have demonstrated that transient elastography is well correlated to liver histology by liver biopsy in diagnosis of liver fibrosis and cirrhosis. Recently, FibroScan is well recognized at various meetings and recommended by many

medical guidelines.

Marianne *et al* studied on 327 patients with chronic hepatitis C, each patient was scoring by METAVIR system, and the median value of LSM for F0-1, F2, F3 and F4 was 5.5 (4.1-7.1) kPa, 6.6 (4.8-9.6) kPa, 10.3 (7.6-12.9) kPa and 30.8 (16.3-48) kPa respectively; and the Area Under ROC (AUR) for F \geq 2, F \geq 3 and F=4 (METAVIR scoring system) was 0.79, 0.91 and 0.97 respectively. Therefore, the LSM varied significantly (P<0.0001) and was significantly related to the liver fibrosis (tau beta of Kendall, 0.55; P<0.0001).

A multi-center and large-sample comparison study between FibroScan and liver biopsy in the chronic hepatitis B patients in China also demonstrated that LSM had good diagnostic accordance rate to the pathological stages. The cut-off value of pathological stages \geq F4 was 17.5 kPa as, the sensitivity and specificity were 0.6 and 0.93 respectively; the cut-off value of pathological stages \geq F3 was 12.4kPa, the sensitivity and specificity were 0.58 and 0.95 respectively; the cut-off value of pathological stages=F2-F3 was 12.4kPa, the sensitivity and specificity were 0.73 and 0.90 respectively; and the cut-off value of pathological stages \geq F2 was 7.3kPa, the sensitivity and specificity were 0.66 and 0.83 respectively.

As stated in the “12th Five-year Plan for Medical Device Technological Industry” (the Ministry of Science and Technology), China will greatly support the research and development of new medical devices and promote the application of Chinese transient elastography system, FibroTouch, which was R&D by Tsing-Hua University independently with new algorithm. FibroTouch can rapidly determine the LSM in a non-invasive way and provide useful information for liver fibrosis staging.

As reported by a recent study on 214 CHB patients in Beijing Friendship Hospital underwent FibroScan testing and FibroTouch testing at the same time. FibroTouch and FibmScan have good consistency in the evaluation of the degree of liver fibrosis. FibroTouch has a significantly higher rate of effective detection (99% vs. 72%) and higher rate of successful detection than FibroScan (100% vs. 97%).

Due to FibroTouch is a new transient elastography system in marketing, there is no too much study on the correlation between FibroTouch and liver biopsy in diagnosis of liver fibrosis and cirrhosis.

II. Study Objective

(I) Primary Objective

Use liver biopsy as “golden standard” for pathological staging, to evaluate the clinical values of FibroTouch for the non-invasive and quantitative diagnosis of liver fibrosis and cirrhosis in CHB patients.

(II) Secondary Objective

- ◆ Difference between FibroTouch and FibroScan in the rate of d successful detection
- ◆ Difference between FibroTouch and FibroScan in the determined values
- ◆ Correlation between determined values of FibroTouch and ultrasonic semi-quantitative scores
- ◆ Performance of FibroTouch.

- Positioning accuracy evaluated by investigators
- Image displaying ability evaluated by investigators
- Scanning speed evaluated by investigators
- Detecting and calculating speed evaluated by investigators

III. Study Goal

To determine the diagnostic accuracy, specificity and sensitivity of FibroTouch for liver fibrosis assessment in CHB patients.

IV. Study Type

It's a prospective and multicenter study.

V. Anticipated Total Cases

According to publications on FibroScan and liver biopsy examination, the mean sensitivity and specificity are 0.61 and 0.90 respectively for different stages (four pathological stages: $\geq F4$, $\geq F3$, $\geq F2$ and F0-F1). Assuming a similar sensitivity and specificity of FibroScan and FibroTouch, the lowest clinically acceptable sensitivity and specificity is 0.55

and 0.8 respectively, when $\alpha=0.05$ and power=80%, 423 cases are required based on sensitivity; total 529 cases are required based on the determination effectiveness=80%; 328 cases are required based on specificity; total 410 cases are required based on the determination effectiveness=80%. By considering the center assignment, ≥ 600 qualified cases are included to guarantee 500 final statistical cases; and ≥ 100 cases are required for S0+S1, S2, S3, S4 and liver cirrhosis (compensatory stage) respectively. For each stage, the case is assigned as equally as possible.

VI. Study Time

One year (from May 2014 to May 2015).

VII. Case Assignment System (via central registration system)

Subject No. is assigned through IWRS system. After the investigator logs in the system and fills in the pathological stages, this system will, according to the completed contents, automatically assign the sole subject No. for this subject.

VIII. Statistical Analysis

Peking University Clinical Research Institute

IX. Study Design

(I) Inclusion Criteria

1. Age: 18—65 years, both gender.
2. History of HBV or HBsAg positive > 6 months up to now.
3. With qualified liver biopsy within three months before or after Fibrotouch examination for pathological staging.
4. Without chemical therapy history of powerful medicine to lower enzyme in the two weeks before blood biochemistry tests (e.g. dimethyl diphenyl bicarboxylate and bicyclol).
5. Participant agreed and signed the informed consent form.

(II) Exclusion Criteria

1. The people who are unable or unwilling to sign informed consent form.

2. The people who have merger of hepatitis c, alcohol and non-alcoholic fatty liver disease, autoimmune liver disease, inherited metabolic liver disease, biliary systemic disease or liver and gall parasitic diseases.
3. The people who have other serious chronic disorders or history of malignancy.
4. The people with ALT ≥ 5 ULN in the past 1 month.
5. The people with $WBC < 3.5 \times 10^9/L$, $PLT < 60 \times 10^9/L$, $PTA < 60\%$.
6. The people with $DBIL \geq 1.5$ ULN.
7. The people with decompensated cirrhosis (especially the people with ascites).
8. Pregnant or lactating women, or women who has a pregnant plan and don't want to birth control in the study period.
9. The people who have wound on the right upper abdomen recently.
10. The people who have various space-occupying tumor or cyst in right liver.
11. The people who have none or limited legal capacity.

(III) Study method

1. Outpatients and inpatients with chronic hepatitis B and compensatory liver cirrhosis, conforming to the inclusion criteria and signing the ICF.
2. Collection of materials and specimen:
 - ◆ Collection of clinical materials: Fill in the uniformly-printed CRF and keep or duplicate the original medical record.
 - (1) Name, sex, age, illness course, family history of infectious diseases and hereditary diseases, drinking history, pharmacotherapy history, and history of chronic diseases (e.g. essential hypertension, heart disease and diabetes).
 - (2) Physical examination: Height (cm), weight (kg), body mass index ($BMI = \text{weight}/\text{height}^2$), heart rate (bpm), respiratory rate (times/min), blood pressure (mmHg).
 - ◆ Retaining of hematological specimen: Within one week before the FibroTouch examination, the venous blood is drawn at an empty stomach, and the different portions of

blood are kept: 2ml whole blood (freeze in two 2ml tubes); 8ml completely-separated serum (freeze in four 2ml tubes); and 3ml plasma (freeze in two 2ml tubes). Keep the tube at -80°C, and uniformly send it to the central laboratory.

◆ Retaining of liver puncture specimen: Fix with 10% neutral formalin, retain additionally 6 white films at every unit, and send it to the pathological examination center (the quality control is shown in Appendix 1).

3. Hematological examination: (the quality control is shown in Appendix 1)

(1) Routine blood tests;

(2) PT, PTA, INR;

(3) TP, ALB, AST, ALT, CHE, GGT, ALP, TBA, TBIL, DBIL, GLU, TC, TG, HDL, LDL, BUN, Cr;

(4) AFP;

(5) Serum virological indices: hepatitis B test (five-item), HBV-DNA assay, HCV antibody test, HIV antibody test; HDV antigen test.

4. Ultrasonic examination:

Within three months after the liver biopsy, the ultrasonic examination is made at an empty stomach for ≥ 8 h. The inner diameter of liver, spleen, gallbladder, portal vein and splenoportal vein is measured through the ordinary two-dimensional ultrasonic examination. The echo data of liver surface/edge/parenchyma and gallbladder wall is scored to evaluate the severity of fibrosis. At every center, the operation should be made via the fixed machine by the fixed person, so as to prevent the artificial error; and the ultrasonic examination, the elasticity determination of liver tissues and the collection of medical history should be made in the same day.

Semi-quantitative Scoring Criteria at Liver Ultrasonic Examination

Score Item	1 score	2 scores	3 scores
Liver surface (Ls)	Smooth, flat	Unsmooth, fine water ripple	Wave, saw-shaped or discontinuous
Liver parenchyma (Lp)	Fine spot, uniform distribution	Slightly enhanced, coarse particle of non-uniform	Obviously echo enhanced, particulate or nodular echo group

		distribution	
Gallbladder wall (G)	Smooth	Coarse, slightly thickened	Obviously thickened or two-side sign

5. Liver Stiffness Measurement (LSM)

Within 3 months before and after the liver biopsy, the liver stiffness measurement (LSM) values are determined via FibroTouch.

◆ Investigators will operate the FibroTouch system to measure the patients' values of liver stiffness and fat attenuation parameters according to the SOP of FibroTouch.

<1>. Subjects lie in face-up position, and stretch his or her right arm to the maximum extent or cross behind his or her head. Enter the name, gender, birth date, medical card No., height, weight and other information into patient information log in FibroTouch system.

<2>. In order to determine accurately, image-guided positioning with ultrasonic B probe should be performed prior to the scanning with liver fibrosis probe. Apply ultrasonic coupling agent to the patient's skin at the position of right side, interspace between the Seventh and eighth rib along the midaxillary line, place the ultrasonic B probe perpendicularly on the skin, and then turn on the FibroTouch image-guided scanning model. Investigator can choose the proper position for liver examination with reference to the ultrasonic B image on the video display screen.

The testing position (at the center line of ultrasonic B image) is selected as following roles:

1. Be away from the heterogeneous liver tissues, such as great vessels, cysts and nodes.
2. Be away from the edge of liver.
3. The position where liver tissue are homogeneous, well-proportioned and with thickness no less than 7cm.

<3>. Save the ultrasonic B image, hang off ultrasonic B probe from the selected position, and change to liver fibrosis scanning model. Hold the fibrosis scanning probe in right hand, bend forefinger to keep probe perpendicularly at the selected position on the skin, lie right elbow on the bed (to avoid the right arm from shaking and moving), and left hand hold the tail of the probe to control the direction. Press the probe slightly on patients' skin to make the pressure indicating strip turn green.

<4>. With subject holding his or her breath slightly, operator observes the liver tissue displayed by ultrasonic-M signal. When the tissue is dark, more homogeneous and laminar distribution, the operators can press down the foot switch, and the fibrosis scanning probe sent out low-frequency shear waves for diagnosing and ultrasonic waves for monitoring, the probe is activated and complete once examination of LSM.

<5>. Ten times of successful detection are performed at the same position. When the inter

quartile range (IQR) value is qualified, the median value of these detections will be considered as the examination result of LSM.

<6>. Save and print the test result.

◆ The operator of FibroTouch must be trained by Hisky and obtain an operating license or certificate.

◆ A successful and effective test by FibroTouch must meet the following requirements: ultrasonic-A signal does not have intensive and rapid shaking, and does not fluctuate significantly in different depth; ultrasonic-M signal does not have big difference of lightness and displays a laminar distribution pattern in different depth; ultrasonic-E signal presents a routine white-and-black twill diagram.

◆ Each subject will obtain 10 successful acquisitions and the median value of these acquisitions will be considered as the examination result of LSM and FAP. The IQR-to-median ratio of the 10 acquisitions should be ≤ 0.3 (the smaller the IQR value, the reliable the result is). If the result is not reliable, it should be detected again until the result is reliable.

◆ To avoid artificial errors, the instrument needs to be operated by a fixed professional in each site, and all information will be documented in a uniform model and stored in U-disk, keep by a designated personnel.

6. FibroScan Examination

6.1 At the same site as that for FibroTouch, the stiffness of liver is determined via Fibroscan at the same day.

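### Section V's 80% power rests on a sensitivity and specificity averaged over three fibrosis thresholds; at each threshold's own cited figures, power to clear both floors is about 18% to 36%.

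*Combined protocol and SAP*

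**What the plan says.** Section V (Anticipated Total Cases) takes from FibroScan publications that "the mean sensitivity and specificity are 0.61 and 0.90 respectively for different stages", and lists four stages: ≥F4, ≥F3, ≥F2 and F0-F1. It assumes FibroTouch performs similarly and sets the floors: "the lowest clinically acceptable sensitivity and specificity is 0.55" "and 0.8 respectively, when" alpha is 0.05 and power 80%. The results are "423 cases are required based on sensitivity" (529 after allowing for 80% effective determinations) and "328 cases are required based on specificity" (410 after the same allowance). Enrolment is at least 600 to secure 500 for analysis, with at least 100 in each of S0+S1, S2, S3, S4 and compensated cirrhosis, as equal as possible.

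The Background gives separate figures from a Chinese multicentre FibroScan study in chronic hepatitis B:

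- ≥F2: "7.3kPa, the sensitivity and specificity were 0.66 and 0.83 respectively"
- ≥F3: "12.4kPa, the sensitivity and specificity were 0.58 and 0.95 respectively"
- ≥F4: 0.60 and 0.93 at 17.5 kPa
- an F2-F3 band: 0.73 and 0.90

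Section IX (VII), Statistical Analysis of Data, takes the different histological grades in turn as the split. For each it builds a ROC curve, chooses a FibroTouch cut-off, and reports sensitivity, specificity and predictive values. It describes no pooled or averaged sensitivity or specificity.

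**The concern.** Detecting ≥F2, ≥F3 and ≥F4 are three different binary tests, each with its own positives and negatives. The mean of their sensitivities is not the operating point of any of them.

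Here the averaging also changes the apparent margins. Against the floors, the averaged pair leaves 0.61 − 0.55 = 0.06 for sensitivity and 0.90 − 0.80 = 0.10 for specificity. The cited pairs leave only 0.83 − 0.80 = 0.03 for specificity at ≥F2 and 0.58 − 0.55 = 0.03 for sensitivity at ≥F3.

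The Study Goal is to determine accuracy, sensitivity and specificity. A reader told that power is 80% would expect each reported threshold to be supported to roughly that degree.

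**Working it through.** **1. Source of 0.61 and 0.90.** Section V does not name its publications, so this match is by arithmetic.

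- Three cumulative thresholds: (0.66 + 0.58 + 0.60)/3 = 0.613 and (0.83 + 0.95 + 0.93)/3 = 0.903.
- Adding the F2-F3 band: (0.66 + 0.58 + 0.60 + 0.73)/4 = 0.6425, which does not round to 0.61.

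The mean is therefore over three thresholds, and F0-F1 contributes nothing.

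**2. The plan's own numbers.** In an exact one-sided binomial test, c is the smallest count with P(X ≥ c | n, p0) ≤ 0.05, and power is P(X ≥ c | n, p1).

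- Sensitivity, 0.61 against 0.55: the smallest n with 80% power is 423 (c = 250, power 80.3%), as stated. A two-sided test would need 538, so the plan's basis is one-sided.
- Specificity, 0.90 against 0.80: the smallest n is 82 (c = 72, power 80.6%). 82/0.25 = 328, as stated, if F0-F1 is a quarter of patients. That share is inferred.
- 423/0.8 = 529 and 328/0.8 = 410.

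**3. The same test with each threshold's cited pair.** Assumptions: 5 × 100 evaluable patients, S and F stages treated as equivalent, S4 plus cirrhosis counted as F4. Positives and negatives are different patients, so power for both floors is the product.

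| Threshold | Positives | Sensitivity vs 0.55 | Power | Negatives | Specificity vs 0.80 | Power | Both |
|---|---|---|---|---|---|---|---|
| ≥F2 | 400 | 0.66 | 99.8% | 100 | 0.83 | 17.7% | 18% |
| ≥F3 | 300 | 0.58 | 26.1% | 200 | 0.95 | >99% | 26% |
| ≥F4 | 200 | 0.60 | 36.1% | 300 | 0.93 | >99% | 36% |

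For 80% power the limiting measure would need 1,043 negatives at ≥F2, 1,696 positives at ≥F3 and 613 positives at ≥F4. The other measure needs 126 positives at ≥F2, 30 negatives at ≥F3 and 44 negatives at ≥F4, all of which are available.

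**4. Sensitivity to the assumptions** (power for both floors, exact; one-sided except in the last row).

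| Layout | ≥F2 | ≥F3 | ≥F4 |
|---|---|---|---|
| 5 × 120 (600 evaluable) | 17% | 31% | 42% |
| 4 × 125 | 19% | 24% | 26% |
| 5 × 100, cirrhosis alone as F4 (100 positives) | 18% | 26% | 24% |
| 423 positives and 328 negatives at every threshold | 38% | 34% | 67% |
| 5 × 100, two-sided 5% | 7% | 16% | 26% |

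The fourth row shows that the shortfall comes from the assumed values and not only from how patients divide between stages. Differences of a point or so, such as 18% against 17% at ≥F2, reflect the discreteness of the exact test.

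**5. Precision.** The 95% half-width is 1.96 × √(p(1 − p)/n).

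- Specificity at ≥F2: p = 0.83, n = 100, 7.4 points.
- Sensitivity at ≥F3: p = 0.58, n = 300, 5.6 points.
- Sensitivity at ≥F4: p = 0.60, n = 200, 6.8 points.

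**6. Dependence on the cut-off.** Assume an equal-variance binormal ROC curve through each cited pair: sensitivity = Φ(d − Φ⁻¹(specificity)), with d = Φ⁻¹(cited sensitivity) + Φ⁻¹(cited specificity). Group sizes are as in step 3.

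- ≥F3 (d = 1.85): at specificity 0.90, sensitivity is 0.71. Power is 99% for specificity and >99% for sensitivity.
- ≥F4 (d = 1.73): at specificity 0.88, sensitivity is 0.71. Power is 98% and >99%.
- ≥F2 (d = 1.37): the best joint power at any cut-off is about 37%.
- A cut-off that equalises the two measures gives Φ(d/2): about 0.82 at ≥F3 and 0.81 at ≥F4, barely above the specificity floor.

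**The case against.** The strongest reply is that the plan contains no test against 0.55 or 0.80 at any threshold. The floors appear only as sizing inputs in Section V, and the analysis section estimates. This stands: missing a floor has no stated consequence, and half-widths of 6 to 7 points are reasonable for estimation. It does not rescue the power claim. An 80% power needs some test, and the individual threshold is the only level at which the plan computes sensitivity and specificity.

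The second reply is that the cited pairs belong to FibroScan cut-offs, whereas the trial will derive new FibroTouch cut-offs. This also stands, and it limits the ≥F3 and ≥F4 results. Step 6 shows that a different point on the same curve could give high power there, or could shift the weakness to specificity. The plan's wording of its cut-off rule is too unclear to say which. At ≥F2 no cut-off on the illustrated curve removes the problem.

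Third, the group counts are inferred from a minimum quota, and the plan does not say whether S4 and cirrhosis together make up F4. The layouts in step 4 cover this without changing the conclusion.

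A reader might go further and infer that no category in the Background reaches 80% power. The documents do not support that: the F2-F3 band (0.73/0.90), with 200 positives and 300 negatives, would clear both floors with power above 99%. It is a band, not a cumulative threshold, and it is not part of the 0.61.

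**Conclusion.** The point holds in a conditional form. The stated 80% power belongs to an average of three thresholds that the trial does not analyse. At the cited operating points, power to clear both floors is about 18% at ≥F2, 26% at ≥F3 and 36% at ≥F4. Each threshold, taken singly, would more likely than not miss a floor.

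This rests on applying the floors at each threshold, a one-sided exact 5% test, 100 evaluable patients per group, and S4 plus cirrhosis as F4. The ≥F2 result is the firmest. The ≥F3 and ≥F4 results hold only at or near the cited cut-offs.

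Two stronger inferences should be avoided. One is that a device as good as the cited one would fail at all three thresholds together: the figures are for each threshold singly, and joint failure was not calculated. The other is that the trial is too small for its purpose: its stated goal is to determine sensitivity and specificity, and for that the precision is adequate. What needs correcting is the power statement.

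**What to change.** In Section V, remove the averaged pair, the list of four stages attached to it, and the single 80% power claim. Replace them with a table by threshold (≥S2, ≥S3, S4) giving:

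- source sensitivity and specificity;
- expected positives and negatives, stating which stage groups make up each threshold;
- power against 0.55 and 0.80;
- expected 95% confidence interval half-width.

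State that power is conditional on the cited operating points and on the assumed group sizes. State that, at those points, only sensitivity at ≥S2 and specificity at ≥S3 and S4 reach 80%. State that specificity at ≥S2 and sensitivity at ≥S3 and S4 are reported as estimates with 95% confidence intervals, with half-widths of about 7, 6 and 7 points.

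Keep enrolment unchanged. The change is to wording and one table, with no extra patients or procedures. Its cost is that the stated power becomes less favourable.

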After signed ICF, the subject's investigational data can be collected. The information in ICF involved in clinical study may be released and monitored by the Sponsor, device regulatory authorities, designated auditors and monitors according to the confidentiality statement.

◆ The following information should be told to the patient: objective and procedure of study; benefits and possible side effects for participation into the clinical study; the privacy of each patient should be protected; and at any study-related injury during this study, the investigators will give the active treatment and the sponsor will make the proper compensation.

◆ Before the initiation of this study, the permission of Ethic Committee should be obtained, and the written certificate for such permission should also be obtained. According to the guideline of GCP, this protocol can be modified only after the permission of Ethic Committee. If such modification may endanger the patient, the contents of ICF should be updated, and the signed consent should be obtained from the participating patients. This study should observe the Helsinki's Declaration and national specifications/regulations on clinical study, and can be made only after the permission of relevant institutions.

(VII) Statistical Analysis of Data

After the determination of study protocol, the statisticians should discuss with the principal investigator on preparing the statistical analytical plan. The data is analyzed through the statistical software SAS 9.3 (authorization No.: 11202165). The sample size is calculated through the software PASS 11. The contents of statistical analysis are classified into the

following parts:

1. Basic description: Age, sex, medical history and relevant indices of laboratory examination (e.g. ALT and AST). For the quantitative indices, the mean, standard deviation, median, minimum value, maximum value, lower quartile (Q1) and upper quartile (Q3) will be described; and for the classification indices, the case amount and percentage in each category will be described.

2. Evaluation of diagnostic ability via elasticity determination result

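### Section V's single 80% power for sensitivity is about right at >=S2 but is not delivered at >=S3 (about 66%) or >=S4 (about 50%), and the basis of its specificity figure of 328 is not documented

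*Combined protocol and SAP*

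**What the plan says.** Section V (Anticipated Total Cases) takes its planning values from published FibroScan work: "the mean sensitivity and specificity are 0.61 and 0.90 respectively for different stages". It sets minimum acceptable values of 0.55 for sensitivity and 0.8 for specificity, with alpha 0.05 and 80% power. The results are:

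- Sensitivity: "423 cases are required based on sensitivity; total 529 cases are required based on the determination effectiveness=80" per cent.
- Specificity: "328 cases are required based on specificity; total 410 cases are required based on the determination effectiveness=80" per cent.

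The section then plans at least 600 patients, who as "qualified cases are included to guarantee 500 final statistical cases". The stage quota is at least "100 cases are required for S0+S1, S2, S3, S4 and liver cirrhosis (compensatory stage) respectively", with stages filled as equally as possible.

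Section IX (VII) says "The sample size is calculated through the software PASS 11". It builds ROC curves using different biopsy grades as the dividing point, and reports sensitivity, specificity and predictive values at the chosen cut-off. It does not compare any result with 0.55 or 0.80.

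Section V does not say which threshold the 80% power refers to, whether the test is one- or two-sided, or whether its cases are all patients or only those positive (or negative) on biopsy.

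**The concern.** Sensitivity is estimated only in patients who are positive on biopsy, and specificity only in those who are negative. Under a fixed stage quota, the number of positives falls as the threshold rises, so one power figure cannot hold at every threshold. The primary objective covers cirrhosis as well as fibrosis, so the higher thresholds matter.

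The stake is interpretation. A reader who takes 80% to apply throughout could treat failure to exceed 0.55 at >=S3 or >=S4 as evidence against the device, when the design had roughly an even to two-in-three chance of showing it even if sensitivity were 0.61. Estimates of AUC, sensitivity and specificity are not themselves affected.

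**Working it through.** **Inputs.** From Section V: sensitivity 0.61 against 0.55; specificity 0.90 against 0.80; alpha 0.05; power 80%; 500 analysed; at least 600 included; at least 100 in each of five strata. The planning values are consistent with the multicentre Chinese FibroScan figures in the background: the mean at >=F4, >=F3 and >=F2 is (0.60 + 0.58 + 0.66)/3 = 0.613 for sensitivity and (0.93 + 0.95 + 0.83)/3 = 0.903 for specificity.

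**Method.** One-sample exact binomial test. For n patients, find the smallest k with P(X >= k | n, p0) <= 0.05. Power is P(X >= k | n, p1).

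**Reproducing 423.** With p0 = 0.55 and p1 = 0.61, the first n with power of at least 80% is 423 (k = 250, actual alpha 0.0495, power 80.3%). A one-sided 0.025 level, as in a two-sided 5% test, would give 538. So 423 is the one-sided 5% number of biopsy-positive patients. Then 423/0.8 = 528.75, which rounds up to 529.

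**The specificity figure.** With p0 = 0.80 and p1 = 0.90, the first n is 82 negatives (k = 72, actual alpha 0.0458, power 80.6%). Two routes lead from 82 to the printed figures:

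- If 80% is the share of positives (four of five equal strata are >=S2): 82/0.2 = 410, and 410 x 0.8 = 328. Here 328 is the number of positives among 410.
- If 25% of patients are negative (one of the four stages listed in Section V): 82/0.25 = 328, and 328/0.8 = 410. Here 328 is a total, whereas 423 is a count of positives.

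Both are exact, so arithmetic cannot choose between them. The 25% is not stated anywhere.

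**Sensitivity power under the quota** (sensitivity 0.61 at every threshold; S4 plus compensated cirrhosis counted as >=S4):

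| Threshold | Positives, 500 analysed | Exact power | Normal approx. | Positives, 600 evaluable | Exact power | Normal approx. |
|---|---|---|---|---|---|---|
| >=S2 | 4 x 100 = 400 | 77.9% | 78.3% | 4 x 120 = 480 | 83.3% | 84.6% |
| >=S3 | 3 x 100 = 300 | 66.2% | 67.5% | 3 x 120 = 360 | 74.6% | 74.4% |
| >=S4 | 2 x 100 = 200 | 47.3% | 52.5% | 2 x 120 = 240 | 54.9% | 59.0% |

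Exact power moves in a sawtooth as n changes. Over n = 190 to 210 it runs from 46.7% to 53.6%, with mean 50.1%, so about 50% is the fair summary at >=S4 with 500 analysed.

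**Specificity power under the quota, 500 analysed.** Negatives are 100, 200 and 300 at >=S2, >=S3 and >=S4; exact power is 87.6%, 99.0% and above 99.9%.

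**The case against.** Four points can be made for the plan.

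*The quota figures are floors.* Section V says at least 600 patients and at least 100 per stratum. With all 600 evaluable, >=S2 reaches 83%. This stands, and is why 80% is called approximately right there. It does not rescue >=S3 (75%) or >=S4 (55-59%).

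*The 328 may be sound.* A reader might infer that it is an error because only 82 negatives are needed. The documents do not support that: 82/0.25 gives 328 exactly, and Section V lists four stages of which F0-F1 is one. What remains is that the basis is undocumented and, on this route, differs from that of 423.

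*500 need not fall short of 529.* A reader might infer a shortfall, but it exists only if the 80% is the share of positives. Read literally, as a rate of valid measurement, 529 is an enrolment figure and at least 600 are enrolled. The literal reading sits awkwardly with the background, where "FibroTouch has a significantly higher rate of effective detection (99% vs. 72" per cent, and with the FibroTouch instruction "If the result is not reliable, it should be detected again until the result is reliable". Yet 80% could be a cautious planning value, so the question stays open.

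*The plan estimates; it does not test.* Section IX (VII) defines no test against 0.55, and the study goal is to determine accuracy. This is fair, and it is why estimation is left alone. But Section V calls 0.55 and 0.80 the lowest acceptable values and sizes the study on them, so its power statement has to be correct, and the analysis should show where the results fall relative to those values.

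**Conclusion.** The concern holds for sensitivity. The single 80% is approximately right at >=S2 (78% with 500 analysed, 83% with 600 evaluable). It is not delivered at >=S3 (66% and 75%) or >=S4 (about 50% and 55-59%).

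This rests on three assumptions: a one-sided 5% exact test, inferred from the match to 423; S4 plus compensated cirrhosis as >=S4; and sensitivity 0.61 at every threshold. A two-sided 5% test would lower power with 500 analysed to about 68%, 53% and 36%. The threshold-specific FibroScan sensitivities in the background (0.66, 0.58, 0.60), taken as truth purely as a scenario, give above 99%, 26% and 36%.

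For specificity the issue is documentation only: 82 negatives are needed, every threshold has at least 100, and power at the planning value is 88% or more. A reader might infer that the trial needs more patients; nothing here requires that. Possible optimism from choosing the cut-off on the same data is a separate matter and is not part of this point.

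**What to change.** Leave enrolment unchanged.

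In Section V:

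1. State that 423 counts biopsy-positive patients and that specificity needs 82 biopsy-negative patients.
2. Name the threshold to which the 80% refers. Replace the single figure with power at >=S2, >=S3 and >=S4 under the quota: for sensitivity about 78%, 66% and 50% with 500 analysed, and 83%, 75% and 55-59% with 600 evaluable; for specificity 88%, 99% and above 99% with 500 analysed. State the assumptions alongside.
3. Have the sponsor confirm from the PASS 11 output the sidedness and what the 80% effectiveness is. Then state the basis of 328. Reconcile 500 final cases with 529 only if the 80% proves to be the share of positives. If the test proves not to be one-sided, recompute the power figures.

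In Section IX (VII): at each threshold, report the lower confidence bounds of sensitivity and specificity against Section V's 0.55 and 0.80.

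The cost is a wording change, one query to the sponsor and a small addition to the analysis. The downside is that the stated power becomes less favourable at >=S3 and >=S4.
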